10.3.4. Reporting of SAE to GSK

SAE Reporting to GSK via Electronic Data Collection Tool

1. The primary mechanism for reporting SAE to GSK will be the electronic data collection tool.
2. If the electronic system is unavailable, then the site will use the paper SAE data collection tool (see next Section) to report the event within 24 hours.
3. The site will enter the SAE data into the electronic system as soon as it becomes available.
4. After the study is completed at a given site, the electronic data collection tool will be taken off-line to prevent the entry of new data or changes to existing data.
5. If a site receives a report of a new SAE from a study participant or receives updated data on a previously reported SAE after the electronic data collection tool has been taken off-line, then the site can report this information on a paper SAE form (see next Section) or to the medical monitor by telephone.
6. Contacts for SAE reporting can be found in the SRM.

SAE Reporting to GSK via Paper Data Collection Tool

- a) Facsimile transmission of the SAE paper data collection tool is the preferred method to transmit this information to the medical monitor.
- b) In rare circumstances and in the absence of facsimile equipment, notification by telephone is acceptable with a copy of the SAE data collection tool sent by overnight mail or courier service.
- c) Initial notification via telephone does not replace the need for the Investigator to complete and sign the SAE data collection tool within the designated reporting time frames.
- d) Contacts for SAE reporting can be found in the SRM.

10.4. Appendix 4: Contraceptive and Barrier Guidance

10.4.1. Definitions

Woman of Nonchildbearing Potential (WONCBP)

Women in the following categories are considered WONCBP:

- Premenopausal female with permanent infertility due to one of the following (for the purpose of this study):
 - Documented hysterectomy
 - Documented bilateral salpingectomy
 - Documented bilateral oophorectomy

For individuals with permanent infertility due to an alternate medical cause other than the above, (e.g., Mullerian agenesis, androgen insensitivity, gonadal dysgenesis), investigator discretion should be applied to determining study entry.

Note: Documentation can come from the site personnel's review of the participant's medical records, medical examination, or medical history interview.

- Postmenopausal female

A postmenopausal state is defined as no menses for 12 months without an alternative medical cause.

- a. A high follicle-stimulating hormone (FSH) level and low oestradiol in the postmenopausal range may be used to confirm a postmenopausal state in women not using hormonal contraception or hormonal replacement therapy (HRT). However, in the absence of 12 months of amenorrhea, confirmation with more than one measurement in line with local thresholds is required.
- b. Females on HRT and whose menopausal status is in doubt must discontinue HRT to allow confirmation of postmenopausal status before study enrolment.

- Male Participants:

Male participants are eligible to participate if they agree to the following during the study intervention period and for **CCI** days after the single dose of study intervention:

- Refrain from donating sperm

Plus either:

- Be abstinent from heterosexual intercourse as their preferred and usual lifestyle (abstinent on a long term and persistent basis) and agree to remain abstinent

OR

- Must agree to use contraception as detailed below
 - Agree to use a male condom and should also be advised of the benefit for a female partner to use a highly effective method of contraception as a condom may break or leak when having sexual intercourse with a woman of childbearing potential who is not currently pregnant

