Malignancy	
As with other immunomodulating agents, GSK3888130B could increase the possibility of immunosuppression resulting in an increased risk of malignancy.
 
Genetic evidence indicates an association between the IL-7R locus and basal cell carcinoma with evidence that an IL-7R missense variant (Thr244Ile) is driving this association. The direction of this mutation is in the opposite direction as that seen in MS where knowledge about the IL-7/IL-7R biology is consistent with activating T cells. Blockade of this biology by GSK3888130B and any consequential risk is unknown.
 
The IL-7R locus is amplified in a number of epithelial solid tumours (5-10%; NSCLC, oesophageal, bladder, cervical) and diverse tumour types (<10%). The functional significance of these amplifications is uncertain as they do not appear to result in increased IL-7R mRNA expression levels.
	
Exclusion: Participants with a history of cancer, including malignant and non-malignant skin cancer.
 
Counselling: Participants will be counselled to follow usual precautions to avoid excessive sun exposure due to a genetic association with basal cell carcinoma.

Reproductive toxicity	
Animal reproductive toxicity studies have not yet been carried out with GSK3888130B. However, there is a theoretical risk that GSK3888130B could affect the development of T and B cells in a developing fetus.
	
Inclusion:
 
 • Only male participants and female participants of non-childbearing potential.

Potential Risk of Clinical Significance	Summary of Data/Rationale for Risk	Mitigation Strategy
		
 Male participants will be required to refrain from intercourse or use a condom, avoid semen exposure to a women of child bearing potential (WOCBP), and refrain from donating sperm for CCI days.
Injection site reactions	
Injection site reactions have been reported for other mAbs and appear to occur more frequently with proteins carrying foreign sequences, such as murine or chimeric mAbs. The reported incidence typically ranges from 1-5%. Serious hypersensitivity reactions are rare.
	
Exclusion: Any participant with a current or past history of clinically significant allergic reactions (anaphylaxis, urticaria) will be excluded.
 
Monitoring: Participants will be closely monitored for injection site reactions.

CCI [REDACTED]

CCI [REDACTED]

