8.3.5. Pregnancy

- Details of all pregnancies in female partners of male participants will be collected after the start of study intervention and until **[REDACTED]** days after the single dose of study intervention.
- If a pregnancy is reported, the Investigator will record pregnancy information on the appropriate form and submit it to GSK within 24 hours of learning of the female partner of a male participant (after obtaining the necessary signed informed consent from the female partner) pregnancy. While pregnancy itself is not considered to be an AE or SAE, any pregnancy complication or elective termination of a pregnancy for medical reasons will be reported as an AE or SAE.
- Abnormal pregnancy outcomes (e.g., spontaneous abortion, foetal death, stillbirth, congenital anomalies, ectopic pregnancy) are considered SAEs and will be reported as such.
- The pregnant female partner will be followed to determine the outcome of the pregnancy. The Investigator will collect follow-up information on the pregnant female partner and the neonate and the information will be forwarded to the Sponsor.
- Any post-study pregnancy-related SAE considered reasonably related to the study intervention by the Investigator will be reported to the sponsor as described in Section 8.3.4. While the Investigator is not obligated to actively seek this information in former study participant's pregnant female partner, he or she may learn of an SAE through spontaneous reporting.

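### The closing clause of the 10.4.1 condom bullet is ambiguous and, on its most workable reading, leaves currently pregnant partners out of a duty that 2.3.1 bases on fetal risk

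*Protocol*

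**What the plan says.** **Protocol 10.4.1 (Appendix 4, male participants).** The list is worded as a condition of entry: "Male participants are eligible to participate if they agree to the following during the study intervention period" and for a redacted number of days after the dose. Men must not donate sperm and must either be abstinent or accept this item: "Must agree to use contraception as detailed below". One bullet sits below it. It begins "Agree to use a male condom and should also be advised of the benefit for a female partner to use a highly effective method" (that is, a contraceptive method), gives condom failure as the reason, and ends "when having sexual intercourse with a woman of childbearing potential who is not currently pregnant". No punctuation separates the condom duty, the advice and the closing clause.

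**Protocol 2.3.1 (reproductive toxicity row).** On the evidence: "Animal reproductive toxicity studies have not yet been carried out with GSK3888130B". On the risk: "there is a theoretical risk that GSK3888130B could affect the development of T and B cells in a developing fetus". The mitigation reads "Male participants will be required to refrain from intercourse or use a condom, avoid semen exposure to a women of child bearing potential (WOCBP", and goes on to bar sperm donation. It contains no exception for a pregnant partner.

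**Protocol 8.3.5.** This section covers the collection and follow-up of partner pregnancies: "The pregnant female partner will be followed to determine the outcome of the pregnancy". It sets no barrier rule.

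**Protocol 5.1.** The Amendment 05 table in 10.9 shows that a criterion on sex and contraceptive or barrier requirements exists. Its current text is redacted.

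**The concern.** A rule meant only to prevent conception can reasonably leave out a partner who is already pregnant. The reason given in 2.3.1 is different: it concerns an effect on a developing fetus. A currently pregnant partner is the case in which that fetus already exists, so leaving her out would run against the stated purpose.

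The practical stake is counselling. Section 10.4.1 is the protocol's contraceptive and barrier guidance, and its list forms part of what men agree to. A man or a member of site staff who works from that bullet alone could conclude that no condom is needed with a pregnant partner, although the 2.3.1 mitigation makes no such exception.

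**Working it through.** No arithmetic applies. The check has three steps.

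**1. Where can the closing clause of 10.4.1 attach?**

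| Attachment | Does it work? | Effect on the condom duty |
|---|---|---|
| (a) The remark that condoms can fail | Nearest in the sentence, but it makes no sense: failure does not depend on whether the partner is pregnant | Unqualified |
| (b) The advice that the partner use a highly effective method | Works in purpose, since a pregnant woman needs no contraception. Awkward in grammar, since the person having intercourse with a woman is the male participant | Unqualified |
| (c) The whole bullet, including the agreement to use a condom | Fits the male subject and the parent item, which speaks of contraception | Limited to partners of childbearing potential who are not pregnant |

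Reading (c) is the most workable, but (b) cannot be excluded.

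**2. Does 2.3.1 cover a pregnant partner?** Its condom item names no partner type, and its semen-exposure item names women of childbearing potential. The visible text spells out that abbreviation but does not define the group. Two things suggest that a pregnant woman belongs to it:

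- The definition of women of non-childbearing potential in 10.4.1 lists permanent infertility and postmenopausal status. Pregnancy is not on the list.
- The words at the end of "when having sexual intercourse with a woman of childbearing potential who is not currently pregnant" would be redundant if women of childbearing potential already excluded pregnant women.

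Both are inferences, but they agree with the fetal rationale.

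**3. Does any other visible text settle it?** Section 8.3.5 deals with reporting and follow-up only. The lifestyle rules in 5.3 do not mention condoms or partners. The 5.1 criterion might settle it, but it cannot be read in this copy.

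**Result.**

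| Partner | 2.3.1 | 10.4.1, reading (b) | 10.4.1, reading (c) |
|---|---|---|---|
| Childbearing potential, not pregnant | Condom | Condom | Condom |
| Currently pregnant | Condom, no exception given | Condom | Not covered |

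The two sections differ only for the pregnant partner, and only on reading (c).

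**The case against.** A reader might infer that 10.4.1 contradicts 2.3.1, or that the protocol permits unprotected intercourse with a pregnant partner. The documents do not support either. Even on the limiting reading, 10.4.1 is silent about that partner; nowhere does it call a condom unnecessary. The provisions are cumulative: a man who follows the condom measure in 2.3.1 also meets the condom item in 10.4.1. At most, 10.4.1 is narrower.

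A reader might also infer that the fetus of a pregnant partner is left unprotected in practice. That cannot be shown. Section 2.3.1 remains in force, the 5.1 text is redacted, and what participants are told at consent is not available. The redaction is not a fault in the plan.

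Two further objections have force. The choice between readings (b) and (c) rests on grammar and context, and no text decides it. In addition, the 2.3.1 mitigation is itself one comma-joined sentence. Its reference to women of childbearing potential may describe the target of the whole measure, so it is not certain that the condom item was meant to cover every partner. A condom duty with partners not of childbearing potential would also go beyond the fetal rationale. The fix is limited for that reason.

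What survives is the ambiguity. A clear rule in 5.1 would not remove it, because 10.4.1 could still be read more narrowly than 5.1 and 2.3.1.

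**Conclusion.** The point holds as an inconsistency in the visible safety wording. The 10.4.1 clause is ambiguous, and its most workable reading makes the eligibility-level condom duty narrower than 2.3.1 by leaving out currently pregnant partners. A gap in protection is not proven.

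The conclusion rests on two assumptions: that the clause attaches to the whole bullet, and that 2.3.1, having no pregnancy exception, covers a pregnant partner.

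The size cannot be quantified. The documents give no figure for partner pregnancies, condom use or passage of the antibody into semen; 2.3.1 calls the risk theoretical, and each participant receives a single dose. No endpoint, sample size or analysis is affected. Severity is minor. The correction is still worth making, because this is a first-in-human antibody for which 2.3.1 reports no animal reproductive toxicity studies yet, and because the repair costs very little.

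**What to change.** Split the 10.4.1 bullet in two:

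1. A male participant who is not abstinent must use a condom during intercourse with any woman of childbearing potential, including a partner who is already pregnant, for the whole restriction period.
2. Because condoms can fail, he should also be advised that a highly effective contraceptive method is of benefit for a partner of childbearing potential who is not pregnant.

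Naming the pregnant partner in item 1 also removes any doubt about whether she counts as being of childbearing potential. Then check that 5.1 and the participant information carry the same rule.

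The cost is one extra bullet and that check, with no added visits, tests or data. The downside is a small burden on men with a pregnant partner who had read 10.4.1 as exempting them; 2.3.1 already asks this of them.

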10.5. Appendix 5: Liver Safety: Required Actions and Follow-up Assessments

Phase 1 liver chemistry stopping criteria have been designed to assure subject safety and to evaluate liver event etiology.

Phase 1 Liver Chemistry Stopping Criteria and Required Follow Up Assessments

Liver Chemistry Stopping Criteria	
ALT-absolute ALT \geq 3xULN If ALT \geq 3xULN AND total bilirubin \geq 2xULN ($>35\%$ direct bilirubin) or international normalized ratio (INR) >1.5 , report to GSK as an SAE ^{1,2} .	
Required Actions, Monitoring and Follow up Assessments	
Actions	Follow Up Assessments
1. Immediately discontinue study intervention 2. Report the event to GSK within 24 hours 3. Complete the liver event form and complete an SAE data collection tool if the event also meets the criteria for an SAE ² 4. Perform liver event follow up assessments as described in the Follow Up Assessment column. Do not restart or rechallenge participant with study intervention 5. Monitor the participant until liver chemistries resolve, stabilise, or return to within baseline (see MONITORING) MONITORING: If ALT\geq3xULN AND total bilirubin \geq2xULN or INR >1.5 6. Repeat liver chemistries (include ALT, aspartate transaminase [AST], alkaline phosphatase, total bilirubin and INR)	
 • Viral hepatitis serology³ 
 • Obtain INR and recheck with each liver chemistry assessment until the aminotransferases values show downward trend • Obtain blood sample(s) for pharmacokinetic (PK) analysis as required, after the most recent dose⁴ • Obtain serum creatine phosphokinase (CPK), lactate dehydrogenase (LDH), gamma-glutamyl transferase (GGT), glutamate dehydrogenase (GLDH) and serum albumin. • Fractionate bilirubin, if total bilirubin \geq2xULN • Obtain complete blood count with differential to assess eosinophilia • Record the appearance or worsening of clinical symptoms of liver injury, or hypersensitivity, on the liver event form • Record use of concomitant medications on the concomitant medications report form including

Liver Chemistry Stopping Criteria	

and perform liver event follow up assessments within 24 hours
 
7. Monitor participant twice weekly until liver chemistries resolve, stabilise or return to within baseline
 
8. A specialist or hepatology consultation is recommended
 
If ALT\geq3xULN AND total bilirubin $<$2xULN and INR \leq1.5:
 
9. Perform liver chemistries (include ALT, AST, alkaline phosphatase, total bilirubin and INR) and perform liver event follow up assessments within 24-72 hours
 
10. Monitor participant weekly until liver chemistries resolve, stabilize or return to within baseline
	
acetaminophen, herbal remedies, recreational drugs, and other over the counter medications.
 
 Record alcohol use on the liver event alcohol intake form 
If ALT\geq3xULN AND total bilirubin \geq 2xULN or INR $>$1.5 obtain the following in addition to the assessments listed above:
 
 Anti-nuclear antibody, anti-smooth muscle antibody, Type 1 anti-liver kidney microsomal antibodies, and quantitative total immunoglobulin G (IgG) or gamma globulins. Liver imaging (ultrasound, magnetic resonance, or computerised tomography) and /or liver biopsy to evaluate liver disease; complete Liver Imaging form. Liver biopsy may be considered and discussed with local specialists if available, for instance: 
 In patients when serology raises the possibility of autoimmune hepatitis (AIH) In patients when suspected drug induced liver injury (DILI) progresses or fails to resolve on withdrawal of study intervention In patients with acute or chronic atypical presentation. If liver biopsy is conducted, then complete liver biopsy form

1. Serum bilirubin fractionation should be performed if testing is available. If serum bilirubin fractionation testing is unavailable, **record the absence/presence of detectable urinary bilirubin on dipstick**, which is indicative of direct bilirubin elevations suggesting liver injury.
2. All events of ALT \geq 3xULN and total bilirubin \geq 2xULN ($>35\%$ direct bilirubin) or ALT \geq 3xULN and INR $>$ 1.5, which may indicate severe liver injury (possible 'Hy's Law'), must be reported to GSK as an SAE (excluding studies of hepatic impairment or cirrhosis); the INR threshold value stated will not apply to participants receiving anticoagulants

3. Includes: hepatitis A immunoglobulin (IgM) antibody; HBsAg and HBcAb; hepatitis C RNA; cytomegalovirus IgM antibody; Epstein-Barr viral capsid antigen IgM antibody (or if unavailable, heterophile antibody or monospot testing) and hepatitis E IgM antibody

Record the date/time of the PK blood sample draw and the date/time of the last dose of study intervention prior to PK blood sample draw. If the date or time of the last dose is unclear, provide the participant's best approximation. If the date/time of the last dose cannot be approximated OR a PK sample cannot be collected in the time period indicated above, do not obtain a PK sample. Instructions for sample handling and shipping are in the SRM

10.6. Appendix 6: SARS-CoV-2 Risk Mitigation Participant Counselling

The risk to participants from SARS-CoV-2 is an evolving situation and dependent on factors such as public health measures, vaccination rates and the effectiveness of vaccination against novel variants. As such, it is impossible to predict how the risk to participants may change over the course of this study. The approach to risk mitigation is informed by UK Government guidance and is broadly described below. Any changes to the advice given to participants will be approved by the Principal Investigator and Medical Monitor, with approval from Competent Authority and ethics committee as required.

[figure not shown]
All study participants:

- Given that the extent of immunosuppression caused by GSK3888130B is unknown, there is the potential that prior vaccination may not provide the same level of protection against infection. Furthermore, it is unknown to what extent GSK3888130B might impair the level of protection provided by vaccines (either to a new pathogen, SARS-CoV-2 variant or as a booster) given after exposure to GSK3888130B and before pharmacodynamic markers return to baseline.
- All participants will be counselled that prior vaccination may not be as effective against circulating infections. The risk of infection is considered low based on prior experience, pre-clinical data and because immunosuppression is expected to be minimal in this single dose study. However, all participants should be vigilant of any new or prolonged symptoms which are suggestive of infection.
- In view of the uncertainty of vaccination and potential variants to SARS-CoV-2, participants must agree to adhere to UK government guidance on international travel during the study period.
- Participants who become eligible for booster vaccinations to SARS-CoV-2 are permitted to receive these during the course of the study in accordance with national or local policy. The sole exception to this would be where participants are offered a live vaccine to SARS-CoV-2 (none currently available in the UK), in view of the risk of activate infection. Participants will be counselled that any booster vaccination may provide less protection due to immunosuppression.
- All participants will be instructed to follow the Public Health England guidance on how to stop the spread of SARS-CoV-2 infection (How to stop the spread of coronavirus (COVID-19) - GOV.UK (www.gov.uk)).
- In the event a participant experiences any signs/symptoms of SARS-CoV-2 infection or other potential infectious disease from the start of study until completed follow-up, they will be instructed to call the phase 1 unit as a matter of urgency for further advice/telephone assessment in the first instance. Early referral to the hospital setting will be considered if a participant is experiencing mild COVID-19 symptoms which is progressing. Hospital referral will be made urgently in the event a participant has moderate/severe disease. Participants who become symptomatic after completion of follow-up should seek medical care through standard pathways (e.g., Accident & Emergency, General Practice).

CD4+ T cell counts $<0.2 \times 10^9/L$ (from detection to resolution)

- Additional study visits and blood tests may be performed at the discretion of the Investigator until CD4⁺ T cell counts return to levels $>0.2 \times 10^9/L$
- Advised to follow the Public Health England Guidance for people previously considered clinically extremely vulnerable from COVID-19 - GOV.UK (www.gov.uk):
 - Follow advice you may receive from your doctor
 - Take care to avoid routine coughs, colds, and other respiratory viruses
 - Follow Public Health England guidance for Living safely with respiratory infections, including COVID-19 - GOV.UK (www.gov.uk).

CCI

